#### Attachment 12: Anticipated Events

An anticipated event is an adverse event (serious or non-serious) that commonly occurs as a consequence of the underlying disease or condition under investigation (disease related) or background regimen.

For the purposes of this study the following events will be considered anticipated events based on reports by healthy subjects in Phase 1 studies:

- headache
- dizziness
- fatigue
- increase of hepatic enzymes

### **Reporting of Anticipated Events**

These events will be captured on the eCRF and in the database, and will be reported to the sponsor as described in Section 12.3.1, All Adverse Events.

Any event that meets serious adverse event criteria will be reported to the sponsor within the appropriate timeline as described in Section 12.3.2, Serious Adverse Events. These anticipated events are exempt from expedited reporting as individual single cases to Health Authorities. However if based on an aggregate review, it is determined that an anticipated event is possibly related to study drug, the sponsor will report these events in an expedited manner.

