The most common treatment emergent adverse events (TEAEs) ( $\geq$ 3 subjects per dose group) in subjects dosed with JNJ-42165279 were headache, dizziness, and fatigue. Overall, more TEAEs were reported with JNJ-42165279 compared with placebo. All the TEAEs were either mild or moderate in intensity. None of the TEAEs was reported as severe and all were considered by the investigator as either doubtfully related or possibly related to the study drug. There were four TEAEs of hepatic enzymes elevated. One subject taking placebo, one woman of non-child bearing potential, and two healthy elderly subjects taking 100 mg JNJ-42165279, had transient elevations of liver transaminases relative to baseline (up to 2.5 times the upper limit of normal) that returned to normal after dosing stopped. No increases occurred in alkaline phosphatase (ALP) or bilirubin. No such increases were observed in the 25 mg cohort. There were no clinically significant changes in any safety measurements, including clinical laboratories, ECGs, vital signs, and physical and neurological examinations. There were no changes or abnormal

findings in blood coagulation parameters. There were no deaths, serious adverse events, or discontinuations due to adverse events. Subjects receiving 100 mg reported slight similarity to sedatives and dissimilarity to stimulants on the Addiction Research Center Inventory-53; no groups reported similarity to cannabinoids. No subjective effects were reported in any of the cohorts by Bond-Lader visual analogue scales.

During the DDI study 42165279EDI1004 sixteen subjects received a single 30-mg JNJ-42165279 dose on Day 1. Thereafter, they received single oral doses of 200-mg itraconazole from Day 4 to Day 10 (inclusive). Subjects also received a dose of 30-mg JNJ-42165279 along with 200 mg itraconazole on Day 8.

Mean plasma JNJ-42165279 concentrations were greater over the entire PK sampling period after co-administration of JNJ-42165279 with itraconazole, compared with administration of JNJ-42165279 alone. Plasma JNJ-42165279 concentrations increased rapidly, with median  $t_{max}$  values of 1.00 hour following administration of JNJ-42165279 with and without itraconazole.

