### 12.2. Special Reporting Situationsa

Safety events of interest on a sponsor study drug that may require expedited reporting and/or safety evaluation include, but are not limited to:

- Overdose of a sponsor study drug
- Suspected abuse/misuse of a sponsor study drug
- Inadvertent or accidental exposure to a sponsor study drug
- Medication error involving a sponsor product (with or without subject/patient exposure to the sponsor study drug, e.g., name confusion)

For this study safety events of interest include diplopia, vision impairment, gait disturbance and severe headache. These events will trigger a neurological examination and a narrative of the event.

Special reporting situations should be recorded in the CRF. Any special reporting situation that meets the criteria of a serious adverse event should be recorded on the serious adverse event page of the CRF.

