### 12.3. Procedures

### 12.3.1. All Adverse Events

All adverse events and special reporting situations, whether serious or non-serious, will be reported from the time a signed and dated ICF is obtained until completion of the subject's last study-related procedure (which may include contact for follow-up of safety). Serious adverse events, including those spontaneously reported to the investigator within 30 days after the last dose of study drug, must be reported using the Serious Adverse Event Form. The sponsor will evaluate any safety information that is spontaneously reported by an investigator beyond the time frame specified in the protocol.

All other events that meet the definition of a serious adverse event will be reported as serious adverse events, regardless of whether they are protocol-specific assessments. Anticipated events will be recorded and reported as described in Attachment 12.

All adverse events, regardless of seriousness, severity, or presumed relationship to study drug, must be recorded using medical terminology in the source document and the CRF. Whenever possible, diagnoses should be given when signs and symptoms are due to a common etiology (e.g., cough, runny nose, sneezing, sore throat, and head congestion should be reported as "upper respiratory infection"). Investigators must record in the CRF their opinion concerning the relationship of the adverse event to study therapy. All measures required for adverse event management must be recorded in the source document and reported according to sponsor instructions.

<sup>a This section has been amended per Amendment INT-2.

The sponsor assumes responsibility for appropriate reporting of adverse events to the regulatory authorities. The sponsor will also report to the investigator (and the head of the investigational institute where required) all suspected unexpected serious adverse reactions (SUSARs). The investigator (or sponsor where required) must report SUSARs to the appropriate Independent Ethics Committee/Institutional Review Board (IEC/IRB) that approved the protocol unless otherwise required and documented by the IEC/IRB. A SUSAR will be reported to regulatory authorities unblinded. Participating investigators and IEC/IRB will receive a blinded SUSAR summary, unless otherwise specified.

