### 16. ETHICAL ASPECTS

### 16.1. Study-Specific Design Considerationsa

Potential subjects will be fully informed of the risks and requirements of the study and, during the study, subjects will be given any new information that may affect their decision to continue participation. They will be told that their consent to participate in the study is voluntary and may be withdrawn at any time with no reason given and without penalty or loss of benefits to which they would otherwise be entitled. Only subjects who are fully able to understand the risks, benefits, and potential adverse events of the study, and provide their consent voluntarily will be enrolled.

The study treatment duration in this study of subjects with SAD is supported by the available toxicology and clinical data (see Investigator's Brochure). A safety signal of reversible mild elevation of liver transaminases was identified in the Phase 1 multiple dose study, occurring in subjects exposed to more than 4 days dosing with 100 mg. To mitigate the risk to subjects participating in this trial, a dose of 25 mg was selected that should allow for testing of the pharmacology of the compound, all subjects will be screened and those with evidence of pre-existing liver dysfunction will not be enrolled, clinical safety labs will be collected every 2 weeks and available for ongoing monitoring by the investigator and sponsor, 'stopping rules' have been developed for stopping treatment in the event that subjects have greater than 3 fold increase in transaminases or have an increase in total bilirubin to  $>2 \times$  ULN, and a Data Review Committee may be established to monitor the study data on an ongoing basis to ensure the continuing safety of the subjects enrolled in this study if the frequency of discontinuations exceeds 10% of subjects or increases of 5 fold over the ULN are observed.

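### Protocol Attachment 12 fills a disease-related list with adverse events seen on the drug in Phase 1, and its single-case exemption conflicts with the SUSAR rules in Section 12

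*Protocol*

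**What the plan says.** Protocol Attachment 12 describes an anticipated event, serious or not, as one that "commonly occurs as a consequence of the underlying disease or condition under investigation (disease related) or background regimen". It continues: "For the purposes of this study the following events will be considered anticipated events based on reports by healthy subjects in Phase 1 studies". The list is headache, dizziness, fatigue and increase of hepatic enzymes.

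Under Reporting of Anticipated Events, the attachment does three things:

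- It keeps serious cases on the normal site-to-sponsor timeline.
- It removes single-case expediting to authorities: "These anticipated events are exempt from expedited reporting as individual single cases to Health Authorities".
- It restores expediting if an aggregate review concludes that the event is possibly related to the drug.

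Section 12.1.1 requires a serious, unexpected event with evidence of a causal link to be reported as a suspected reaction, and leaves expectedness to the Investigator's Brochure. Section 12.3.1 states: "A SUSAR will be reported to regulatory authorities unblinded". The same section directs that anticipated events be handled according to Attachment 12.

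On the signals themselves, Section 16.1 says: "A safety signal of reversible mild elevation of liver transaminases was identified in the Phase 1 multiple dose study". Section 12.2 says: "For this study safety events of interest include diplopia, vision impairment, gait disturbance and severe headache".

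**The concern.** The attachment sets one criterion for the list and fills it by another. A category meant for events of the illness is filled with events that the protocol elsewhere reports on the study drug, including the one it calls a safety signal. The classification carries a consequence: the listed terms lose single-case expedited reporting, and the terms have no severity limit.

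At stake is how quickly a regulator hears of a serious liver-enzyme or headache case in a trial that was suspended once already, in January 2016 (SAP Section 1). If staff treat the specific attachment as overriding the general SUSAR rule, such a case could wait for a review that the protocol does not describe.

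**Working it through.** There is no plan figure to reproduce. The check sets the texts side by side.

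**1. Does the list meet its own definition?**

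- The definition requires the underlying disease or a background regimen as the source.
- The stated basis is reports from healthy subjects, who did not have social anxiety disorder. The protocol describes no background regimen, and Section 8 prohibits other psychiatric medication.
- In Section 1.1, the most common treatment-emergent events in the second multiple-dose study in "subjects dosed with JNJ-42165279 were headache, dizziness, and fatigue". More such events were reported on drug than on placebo, with attribution judged doubtful or possible.
- In the same study there were four hepatic-enzyme events: three on 100 mg and one on placebo.
- SAP Section 8.2 singles out headaches and liver-function events for subject-level plots, so the analysis plan also follows them as safety topics.

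The list does not follow from the definition.

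**2. How strong is the Phase 1 liver evidence?** The study had four cohorts, each with 6 subjects on active drug and 2 on placebo.

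- All active doses: 3/(4 × 6) = 3/24 = 12.5%. Placebo: 1/(4 × 2) = 1/8 = 12.5%. Fisher's exact p = 1.0.
- The two 100 mg cohorts only: 3/(2 × 6) = 3/12 = 25%, against 1/8. Fisher's exact p = 0.62.

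These counts do not establish causation. The point rests on the protocol's own description of the finding as a safety signal, not on a demonstrated excess.

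**3. How many named signals does the exemption reach?** The protocol names five: four events of interest in Section 12.2 and transaminase elevation in Section 16.1. The Attachment 12 terms cover two of them, since headache includes severe headache and hepatic enzyme increase covers transaminases. That leaves 5 − 2 = 3 untouched: diplopia, vision impairment and gait disturbance.

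**4. What happens to a serious hepatic-enzyme increase judged possibly related?**

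| Status in the Investigator's Brochure | Sections 12.1.1 and 12.3.1 (SUSAR) | Attachment 12, through 12.3.1 | Result |
|---|---|---|---|
| Listed at that nature and severity | Not a SUSAR | Exempt as a single case | No conflict |
| Not so listed | Report to authorities, unblinded | Exempt as a single case until aggregate review | Conflict |

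Nothing says which rule prevails in the second row. The same table applies to a serious headache. In the two Phase 1 studies whose safety results Section 1.1 describes, there were no serious adverse events. Enzyme rises in the multiple-dose study reached at most 2.5 times the upper limit of normal. A serious case would therefore exceed anything the protocol describes; whether it would exceed the Brochure cannot be told from these documents.

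**5. What triggers the fallback?** The attachment gives no owner, frequency, threshold or blinding status for the aggregate review. Individual attribution of possible or stronger is enough in Section 12.1.1 to call an event drug-associated, but is not enough to lift the exemption.

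**The case against.** A reader might infer that serious cases of the trial's named signals simply go unexpedited. The documents do not support that. Attachment 12 restores expediting after aggregate review, three of the five signals are not listed, and the SUSAR rules carry no exception for anticipated events. What exists is a conflict between texts, not a clear removal of expediting. It arises only where the Brochure does not list the event at that nature and severity, and the Brochure is not available here.

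Three further readings also go too far:

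- **That Section 12.2 marks severe headache for possible expedited reporting.** That wording introduces a general list (overdose, misuse, accidental exposure, medication error). The consequence stated for severe headache is a neurological examination and a narrative.
- **That none of the four terms could come from the illness.** Comorbid MDD and GAD are allowed, and the HDRS17 form in Attachment 1 includes headaches and fatigability among its symptoms. Headache and fatigue might be justified on that ground, but the attachment does not use it.
- **That the liver stopping rules were a response to the suspension.** Amendment INT-1 presents its change as a clarification, and its date of April 2015 precedes January 2016.

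Other safeguards stand. Serious events go to the sponsor within 24 hours, sponsor medical monitoring is continual (3.3.2), and Section 16.1 provides for safety laboratory tests every two weeks. Section 11.8 says that a Data Review Committee will be set up if relevant new findings emerge, and nothing makes the aggregate review depend on that committee.

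All of this narrows the consequence. None of it resolves the mismatch between definition and list, or says which reporting instruction governs.

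**Conclusion.** Attachment 12 is wrong as written on two counts: the list contradicts the definition above it, and the exemption conflicts with Sections 12.1.1 and 12.3.1 for any listed event that qualifies as a SUSAR. In practice this matters most for two of the five named signals, liver enzymes and headache.

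The mismatch can be read directly from the text and needs no assumption. The reporting conflict is conditional on a case being serious, suspected of being drug-related, and unexpected under the Brochure; how often that would happen cannot be estimated from the documents. The possible harm is a delayed individual report to authorities, not loss of the case, because the sponsor receives it on the ordinary timeline. No estimate, power figure or SAP analysis changes. The correction is worth making because it is cheap and concerns patient safety.

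**What to change.** Reconcile Attachment 12 with Sections 12.1.1 and 12.3.1:

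1. State in Attachment 12 that the exemption never applies to an event meeting the SUSAR definition, with expectedness judged by the Investigator's Brochure as Section 12.1.1 provides.
2. Remove hepatic enzyme increase from the list.
3. Keep headache, dizziness or fatigue only if each is justified as arising from social anxiety disorder or comorbid MDD or GAD, and replace the Phase 1 rationale accordingly. Otherwise state that no anticipated events are specified.
4. If any term remains, say who conducts the aggregate review and when.

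The cost is protocol wording in one attachment and any matching safety-reporting instructions, with possibly a few more single-case expedited reports. The SAP needs no change, since none of its analyses uses the list.

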#### Attachment 13:

### Prohibited Cytochrome P450 Inhibitors and Inducers

#### Inducers

Carbamazepine Dexamethasone Efavirenz Ethosuximide Isoniazid Nevirapine Phenobarbital Phenytoin Prednisone Rifabutin/rifampicin St. John's Wort

#### Inhibitors

Amprenavir Atazanavir Clarithromycin Clotrimazole Darunavir Delavirdine Diltiazem Elvitegravir/Cobicistat Erythromycin Fluconazole Fluoxetine Fluvoxamine Fosamprenavir Grapefruit Indinavir Itraconazole Ketoconazole Lopinavir Metronidazole Mibefradil Miconazole Nefazodone Nelfinavir Nifedipine Norfloxacin Omeprazole Propoxyphene Quinine Ritonavir Saquinavir Seville oranges Simeprevir Tipranavir Troleandomycin Verapamil Zafirlukast

#### LAST PAGE

### LAST PAGE

HAM-D ₆	6-item subscale derived from the HDRS ₁₇
HDRS ₁₇	17-item Hamilton Depression Rating Scale
HR	heart rate
ICH	International Conference on Harmonization
ITT	Intent-to-Treat
IVRS	interactive voice response system
IWRS	interactive web response system
LSAS	Liebowitz Social Anxiety Scale
MDD	major depressive disorder
MedDRA	Medical Dictionary for Regulatory Activities
MOS Sleep-R	Medical Outcomes Study- 12-item Sleep Scale Acute - Revised
OEA	oleylethanolamide
PD	pharmacodynamic
PEA	palmitoylethanolamide
PK	pharmacokinetic(s)
Q-LES-Q	Quality of Life, Enjoyment, and Satisfaction Questionnaire
SAD	social anxiety disorder
SAE	serious adverse event
SAP	statistical analysis plan
SD	standard deviation
SDS	Sheehan Disability Scale
SHAPS	Snaith-Hamilton Pleasure Scale
SI	standard international
SIGH-A	Structured Interview Guide for the Hamilton Anxiety Scale
TEAE	treatment-emergent adverse event
TEMA	treatment-emergent abnormality

1. INTRODUCTION

In January 2016, Janssen had decided to suspend the 42165279SAX2001 study (see the press release on 18 January 2016 on Janssen.com). The study was unblinded and the randomization codes were provided to the investigators so that the patients could be informed about their treatment. Safety information was analyzed, and a separate Statistical Analysis Plan (SAP) was written and approved for the interim safety analysis. No efficacy data was analyzed, and datasets containing efficacy information of the subjects who were unblinded at trial suspension will remain in a secure location at the data management department until final DB lock (see Partial Database Lock Notification form dated 24 March 2016 and Note to File dated 15 December 2016).

This SAP contains definitions of analysis sets, derived variables, and statistical methods for the final analysis of efficacy, biomarker and safety data. The final analysis will include subjects who were enrolled prior to study suspension and subjects who were enrolled after the study had resumed. See Section 2.5 for a definition of the analysis sets.

1.1. Trial Objectives

The primary objective of this study is to investigate the efficacy of JNJ-42165279 during 12 weeks of treatment in subjects with social anxiety disorder (SAD).

The secondary objectives of this study are:

- To assess the safety and tolerability of JNJ-42165279 in subjects with SAD.
- To assess the plasma pharmacokinetic (PK) profile of JNJ-42165279 administered as once daily (*qd*) in subjects with SAD using a population PK approach, and explore the relationship between exposure to JNJ-42165279 and efficacy and safety parameters.

The exploratory objectives are:

- To assess the efficacy of JNJ-42165279 on both anxiety and depression symptoms.
- To evaluate the impact of treatment with JNJ-42165279 compared to placebo on patient-reported assessments of symptoms of anxiety, depression, impairment in daily living and quality of life.
- To evaluate pharmacodynamic (PD) effects by the assessment of biomarkers of peripheral pharmacological activity after repeated doses of JNJ-42165279, including assessment of plasma concentrations of fatty acid amides (FAAs) (anandamide [AEA], palmitoylethanolamide [PEA], and oleoylethanolamide [OEA]) that are expected to rise as a consequence of the inhibition of their hydrolysis by fatty acid amide hydrolase (FAAH).
- To explore the relationship between plasma PK and plasma concentrations of FAAs (AEA, PEA and OEA) in subjects with SAD.
- To explore any potential differences between healthy subjects and subjects with SAD using a population PK approach.

1.2. Trial Design

This is a multi-center, double-blind, placebo-controlled, randomized, parallel-group study assessing the efficacy, safety, and tolerability of JNJ-42165279 during 12 weeks of treatment in subjects with SAD.

Approximately one-hundred twenty-two (122) subjects will be enrolled in this 12 week treatment study randomly assigned in a 1:1 ratio to either 25 mg of JNJ-42165279 or placebo (dosed once daily orally).

For all enrolled subjects, this study will consist of a 28-day eligibility screening period, a 12 week double-blind treatment period and a follow-up examination between 7 and 28 days after last dose. The study duration for each subject will be maximally 20 weeks.

The study will be an outpatient study.

1.3. Statistical Hypotheses for Trial Objectives

The primary efficacy endpoint for this study is the reduction of symptom burden associated with social anxiety disorder (SAD), as measured by the change from baseline to the 12-week endpoint in the Liebowitz Social Anxiety Scale (LSAS) total score. The null hypothesis to be tested to address the primary objective is that there is no difference between JNJ42165279 and placebo based on the primary efficacy endpoint.

1.4. Sample Size Justification

The sample size for the study is based on the assumption of a treatment difference of at least 10 points in the mean change from baseline to the endpoint in LSAS total score between JNJ-42165279 treatment group and placebo. A standard deviation of 24 in the change in LSAS total score from baseline is used based on published data.^{7,10,11} To detect the treatment difference of 10 points (which is judged to be clinically relevant^{7,10,11}) with a power of 90% at an overall 1-sided significance level of 0.20, 53 subjects in each group are required. When adjusted for a drop-out rate of approximately 15% of subjects, the required number of subjects is 61 per treatment group.

The impact of this sample size (N=122) on the JNJ- 42165279 effect size to be detected for the other continuous secondary and exploratory endpoints for different values of significance level and power, assuming a drop-out rate of 15%, are presented in [Table 1](#).

Table 1: JNJ-42165279 effect size to be detected for different values of significance level and power, assuming a drop-out rate of 15%

I-sided significance level	Power	Effect size to be detected
0.10	80%	0.4
0.10	90%	0.5
0.20	80%	0.3
0.20	90%	0.4

